#### 8.5.7.5 Other endpoints associated with asthma exacerbations

##### Proportion of subjects with $\geq 1$ asthma exacerbation

The proportion of subjects with  $\geq 1$  asthma exacerbation during the 52 weeks of treatment will be addressed as a supportive variable to the primary objective. The proportion of subjects in the active tralokinumab arm will be compared with the proportion in the placebo group in both populations using a Cochran–Mantel–Haenszel test controlled for stratifying variables.

The results of the analyses will be presented as weighted difference in the proportion of subjects who have  $\geq 1$  asthma exacerbation, together with associated 95% CI and 2-sided p-value for each active dose regimen versus placebo. The number and percentage of subjects with  $\geq 1$  asthma exacerbation will also be summarized by randomized treatment for both populations.

##### Time to first asthma exacerbation

Time to first asthma exacerbation will be analyzed as another supportive efficacy variable to the primary objective to explore the extent to which treatment with tralokinumab delays the time to first exacerbation compared with placebo. A Cox proportional hazard model will be fitted to data with including treatment and at least stratifying variables as covariates.

Results of the analysis will be summarized as hazard ratios, 95% confidence intervals and p-values.

Time to first asthma exacerbation will be displayed graphically using a Kaplan-Meier plot. The median time to event will be summarized by randomized treatment, if there is sufficient uncensored data available to calculate these median values. The percentage of subjects who are exacerbation free at 22 and 44 Weeks will be estimated for each treatment group.

#### **8.5.7.6 Emergency room or urgent care visits and hospitalizations due to asthma**

Annual rate of asthma exacerbations that are associated with an ER or urgent care visit or a hospitalization will be analyzed using a similar negative binomial model as outlined for the primary efficacy variable in Section 8.5.6.

#### **8.5.7.7 Health care resource utilization and productivity loss due to asthma**

##### **WPAI-CIQ**

The WPAI+CIQ data will be summarized by treatment, including the 4 types of scores: absenteeism, presenteeism, work/class productivity loss, and activity impairment described. The number and percentage of subjects with asthma specific resource utilization (defined in Section 8.4.3.8) will be presented by treatment group.

#### **8.5.7.8 Asthma symptom, general health-related quality of life and asthma control**

This section specifies analyses addressing the secondary objectives other than the key secondary objectives described in Sections 8.5.7.2, 8.5.7.3 and 8.5.7.4.

##### **Nights with awakening due to asthma**

The number of nights with awakening due to asthma and requiring rescue medication will be summarized and analyzed in the same way as rescue medication use, below.

##### **Rescue medication use**

Total rescue medication use (average puffs/day) will be analyzed as the response variable by fitting a linear model to the data. Treatment group will be fitted as the explanatory variable, and at least stratifying variables will be fitted as covariates. The results will be presented in terms of LSMEANS, difference between treatments in LSMEANS and 95%CI. The number and percentage of subjects within each treatment group who received rescue medication will be summarized by visit.

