The final follow up visits (i.e., 30 and 31) are to occur 4 weeks (+7 days) and 20 weeks (+7 days) from the date of the EOT visit, respectively.

Subjects who prematurely discontinue IP (see section 3.9) should return to the study site and complete procedures described for the IP Discontinuation Visit (IPD visit), see Table 1.

At the IP discontinuation visit, the subject will be given three options as to how they will be followed up:

1. Ideally, the subject should return for all regular clinic visits and perform all scheduled assessments until he/she completes a total of 52 weeks in the study, or,
2. The subject will be followed up on a monthly basis via telephone calls while continuing eDiary completion, until the subject completes 52 weeks in the study. No further procedures will be performed. Or,
3. The subject will be contacted at 52 weeks post randomization. No other study assessments will be performed prior to this contact.

For each option, an EOT visit will be conducted.

For option 1, all procedures will be done at each visit as indicated in Table 1. For options 2 and 3, AEs/SAEs, changes in concomitant medications and asthma exacerbation information are the minimum elements that must be collected at each contact.

The subject's decision needs to be documented in the eCRF and the specific section in the ICF/assent form addendum needs to be signed by the subject.

Should the subject choose option 2 or 3 above, they will complete the IP Discontinuation visit immediately and then a follow up telephone call at week 52. If the subject chooses option 1, they will complete the IP Discontinuation visit immediately and then the EOT visit at week 52. The EOT visit/call will be completed immediately in the case of early withdrawal from option 1 or 2.

Subjects who initially chose options 1 or 2 and subsequently cannot or do not wish to comply with the requirements of the chosen option, can choose to continue with a less invasive option (i.e.: Subject initially choosing option 1 can continue with 2 or 3, subjects initially choosing option 2 can continue with 3).

Subjects who do not wish to have any follow up contacts at all, will be discontinued from the study. All discontinued subjects must return the ePRO and ePEF devices at the EOT visit.

Completion, or early termination of IP treatment, will be registered via the IWRS/IVRS for each subject.

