#### **8.4.3.1 Asthma symptom score**

Asthma symptoms during night-time and daytime will be recorded by the subject each morning and evening in the Asthma Daily Diary. Symptoms will be recorded using a scale 0-3, where 0 indicates no asthma symptoms. Asthma symptom daytime score, night-time score, and total score will be calculated separately.

The total daily symptom score will be calculated by taking the sum of the daytime and night-time asthma symptom scores for each day. If a subject is missing a value for either daytime or night-time asthma symptom score on a given day then the total score for that day will be set to missing.

The key secondary outcome variable is the biweekly mean daily asthma symptom total score. The daily asthma symptom total score is defined as the sum of the daytime and night-time symptom scores as captured in the Asthma Daily Diary. The biweekly mean is calculated as the mean daily asthma symptom total over 14 sequential days. If more than 7 daily scores (>50%) within that period is missing, then the daily asthma symptom mean score is set to 'missing'.

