#### **8.4.3.2 Rescue medication use**

The number of rescue medication inhalations and nebulizer treatments taken will be recorded by the subject in the Asthma Daily Diary twice daily.

The number of inhalations of rescue medication captured in the eDiary each day will be calculated per subject. If a subject is missing a value for either morning or evening rescue medication on a given day, then the total rescue medication use for that day will be set to missing.

Total rescue medication use, defined as the average number of inhalations (puffs) per day will be calculated as the outcome variable.

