#### 8.5.7.2 Asthma symptoms

**The key secondary outcome variable:** Change from baseline in bi-weekly mean daily asthma symptom score (combined daytime and night-time score as captured in the Asthma Daily).

The change from baseline in asthma symptom total score, daytime score, and night-time score at Week 52 will each be summarized and analyzed using the repeated measurement approach defined for change from baseline in pre-dose/pre-BD FEV1, as described in Section 8.4.2.4. Included in the model will also be the baseline mean daily asthma symptom score.

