##### **Home PEF (morning and evening)**

Change from baseline in morning and evening PEF at Week 52 will each be summarized and analyzed using a similar model as the model for change from baseline in pre dose/pre-BD FEV1, as described in Section 8.5.7.1

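### Rescue medication use and nights with awakening are analysed as what reads as one average per subject in a linear model, so a short early diary counts as much as a full 52 weeks; symptom score and home PEF from the same diary use repeated measures

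*Protocol*

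**What the plan says.** Section 8.4.3.2 defines the outcome: "Total rescue medication use, defined as the average number of inhalations (puffs) per day will be calculated as the outcome variable". Its only missing-data rule works at day level. If the morning or evening entry is absent, "then the total rescue medication use for that day will be set to missing". It states no averaging period and no minimum number of days.

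Section 8.5.7.8 gives the analysis: "Total rescue medication use (average puffs/day) will be analyzed as the response variable by fitting a linear model to the data". The terms are: "Treatment group will be fitted as the explanatory variable, and at least stratifying variables will be fitted as covariates". It names no visit, no treatment-by-visit interaction, no covariance structure and no baseline. The entry just above it, on nights with awakening due to asthma, refers to the rescue medication analysis for its method.

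Two other endpoints from the Asthma Daily Diary are handled differently:

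- Symptom score (section 8.5.7.2) is "analyzed using the repeated measurement approach defined for change from baseline" in FEV1, with its baseline score added to the model. It is built from 14-day means under an explicit rule in section 8.4.3.1: "If more than 7 daily scores (>50%) within that period is missing, then the daily asthma symptom mean score is set to 'missing".
- Home PEF (section 8.5.7.8): "Change from baseline in morning and evening PEF at Week 52 will each be summarized and analyzed using a similar model" to the FEV1 model.

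The FEV1 model in section 8.5.7.1 has categorical visit, treatment by visit and an unstructured covariance matrix.

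Section 4.2 gives three follow-up options after stopping investigational product. Option 1 keeps all visits and assessments, and option 2 keeps the eDiary going to Week 52. Option 3 is a single contact at 52 weeks: "No other study assessments will be performed prior to this contact".

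**The concern.** Diary length will differ between subjects. Some withdraw from the study, and some stop treatment and choose option 3. With a single average per subject, a record of a few early weeks enters the model with the same weight as a 52-week record. Early weeks come before the treatment effect has fully developed and before any later change in rescue use, so they are not a fair stand-in for the year.

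A repeated measures analysis of bi-weekly means avoids this. Each period's difference is estimated from the data of that period, together with the correlation to earlier periods. It remains valid when leaving depends on values already recorded. The protocol applies that approach to symptom score and home PEF and gives no reason for departing from it here.

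Nothing else in the protocol would expose the problem. Section 8.5.2 limits its missing-data sensitivity analyses to the primary and key secondary endpoints.

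At stake are the estimates for two other secondary diary endpoints in both populations, and their comparability with the other two diary endpoints.

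**Working it through.** **Inputs from the protocol.** 385 subjects per arm and a uniform loss to follow-up of 15% (section 8.2). No mean, SD or effect size for rescue use is given, so the rest is an illustration on stated assumptions.

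**The plan's own figure first.** Uniform loss of 15% removes on average half of each leaver's time: 385 × (1 − 0.15/2) = 356.1 subject-years per arm, against about 355 stated. The figure reproduces. The same arithmetic leaves 7.5% of planned diary time unobserved if diary exit equals that loss. Diary exit could be higher, because option 3 still yields exacerbation information at Week 52 but no diary. An exit of 30% is therefore also shown, as an assumption.

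**Assumptions.** The treatment effect builds linearly to Week R and is then flat: r(w) = min(w/R, 1) for w = 1 to 52. A leaver's last diary week is uniform on 1 to 52 and unrelated to rescue use.

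**Formulas.**
- F = mean of r(w) over 52 weeks (the true 52-week difference as a share of the full effect).
- C = mean over w of the running average of r up to week w (what a leaver's average shows).
- With exit proportion d equal in both arms, the share of the true difference retained is 1 − d × (1 − C/F).

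For R = 26, F = (13.5 + 26)/52 = 0.760. The running average is (w + 1)/52 up to Week 26 and 1 − 12.5/w afterwards, so C = (7.25 + 17.45)/52 = 0.475. At d = 0.15 the share retained is 1 − 0.15 × (1 − 0.475/0.760) = 0.944.

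| Build-up to Week | F | C | Retained, 15% exit | Retained, 30% exit (assumed) |
|---|---|---|---|---|
| 12 | 0.894 | 0.690 | 96.6% | 93.1% |
| 26 | 0.760 | 0.475 | 94.4% | 88.8% |
| 52 | 0.510 | 0.264 | 92.8% | 85.6% |

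The shrinkage is 3.4% to 7.2% at 15% exit and 6.9% to 14.4% at 30%.

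**Unequal exit.** Suppose placebo improves by 1.0 puff/day and active by 1.5, with R = 26. The true 52-week difference is 0.5 × 0.760 = 0.380. An arm with improvement m and exit d shows m × [(1 − d)F + dC].

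| Exit, active / placebo | Difference obtained (true 0.380) |
|---|---|
| 15% / 15% | 0.358 |
| 10% / 20% | 0.394 |
| 5% / 25% | 0.430 |
| 20% / 10% | 0.323 |

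For the 10%/20% row: 1.5 × (0.9 × 0.760 + 0.1 × 0.475) − (0.8 × 0.760 + 0.2 × 0.475) = 1.097 − 0.703 = 0.394.

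**What the alternative gives in the same set-up.** Because exit here is unrelated to rescue use, subjects still in the diary in each period show that period's true difference. The equally weighted average over the 26 periods therefore returns 0.380, apart from a small edge effect in the period in which a subject leaves.

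**The case against.** The strongest reply is that much of this belongs to the SAP. Section 8.4.1.2 defers detailed visit and period windows to it. The averaging period and a minimum-days rule are ordinary SAP derivations, and the model terms are stated as a minimum, so baseline could still be added. Home PEF has no minimum-days rule in the protocol either. A subject-level average over treatment is also a legitimate summary, and different models for different endpoints do not contradict each other. All of that stands: the absence of detail is not the complaint. What remains is the choice that the protocol does make, a linear model on an average, when a better-behaved model is already planned for the same diary.

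Little rides on it. Rescue use is outside the testing hierarchy of section 8.5.1, and section 8.5.7.8 promises LS means and confidence intervals without a p-value. Daily rescue use is also an item of ACQ-6, a key secondary endpoint analysed by repeated measures with sensitivity analyses. This also stands, and it keeps the point minor.

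A reader might go further in four ways that the protocol does not support:

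- **That every other diary endpoint uses repeated measures.** Nights with awakening share the linear model, so the four diary endpoints split two and two.
- **That the analysis is biased toward no effect.** With unequal exit the error runs in either direction.
- **That the average is taken at Week 52, so early leavers drop out as in a complete-case analysis.** The loss could be larger on that reading, but the rescue medication text names no Week 52 target, whereas the home PEF text does.
- **That everyone who stops treatment leaves the diary.** Options 1 and 2 keep it going to Week 52.

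**Conclusion.** The point holds as a cheap improvement. For rescue medication use and nights with awakening, the protocol fixes a method that lets a short early record stand for the year, while a suitable model is already specified for symptom score and home PEF. No stated sensitivity analysis would show the effect.

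The size is modest: about 3% to 7% shrinkage of the 52-week difference at 15% equal uniform exit, and error in either direction when exit differs between arms. These figures rest on three assumptions: a linear build-up of effect, exit unrelated to rescue use, and the reading that the average spans each subject's available treatment-period diary. The protocol does not state that span, but it is the natural reading. Exit driven by rescue use is not quantified here. Primary and key secondary conclusions are unaffected.

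**What to change.** 1. In section 8.4.3.2, define bi-weekly mean puffs per day over 14 sequential days, set to missing when more than 7 of the 14 days are missing, as section 8.4.3.1 does for the symptom score.
2. In section 8.5.7.8, analyse change from the bi-weekly diary baseline already defined in section 8.4.1.1 (study days −14 to −1) with the existing repeated measures model, including baseline as a covariate.
3. Report the equally weighted average difference over the 26 periods, which keeps the 52-week average as a target, and the Week 52 difference.
4. Treat nights with awakening in the same way, since their analysis is defined by reference to rescue use.
5. Keep the simple subject average as a descriptive summary.

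The cost is a wording change and slightly more analysis work on other secondary endpoints. No new data are needed. An unstructured matrix over 26 periods has 26 × 27/2 = 351 parameters and may not converge in the smaller biomarker positive population. The symptom score model already faces this, and the compound-symmetry fallback in section 8.5.7.1 would apply here too.

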## **8.4 Outcome measures for analyses**

### **8.4.1 General Definitions**

#### **8.4.1.1 Definition of baseline and subject baseline variables**

For spirometry variables the measurement recorded at the baseline visit (Visit 3) will be used as baseline. If the Visit 3 measurement is missing, the last non-missing value before Visit 3 will be used as baseline instead. For post-BD FEV1, the measurement after the first BD administration is the baseline.

The baseline for the ePRO variables (ACQ-6, AQLQ(s)+12, WPAI-CIQ, and EQ-5D-5L) will be captured on the ePRO device at Visit 3. Baseline for Asthma Daily Diary variables will be the bi-weekly mean for data collected between study day -14 and -1 (i.e. 14 to 1 day before Visit 3).

For laboratory data and physical examination, baseline will be defined as the latest non-missing assessment prior to first dose.

Absolute change from baseline outcome variables is computed as (post-randomization value – baseline value).

Percent change from baseline is computed as  $((\text{post-randomization value} - \text{baseline value}) / \text{baseline value}) \times 100\%$ . If either the post-randomization value or the baseline value is missing, then the absolute or percent change from baseline value will also be set to missing.

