#### 8.5.7.4 ACQ-6 defined asthma control

**The key outcome variable:** Change from baseline in ACQ-6.

Change in mean score from baseline for ACQ-6 will be summarized and analyzed using the repeated measurement approach defined for change from baseline in pre-dose/pre-BD FEV1, as described in Section 8.4.2.4. Included in the model will also be the baseline ACQ-6 mean score.

**Supportive outcome variable:** ACQ-6 responder (yes/no).

Responder variables ACQ-6 (yes/no) will be analyzed using a logistic regression model with covariates of at least treatment, stratifying variables, and baseline value.

The number and percentage of subjects achieving mean ACQ-6  $\leq 0.75$ ,  $0.75 < \text{mean ACQ-6} < 1.5$  and mean ACQ-6 of  $\geq 1.5$  at EOT will be summarized by treatment. Additionally, the number and percentage of subjects achieving an improvement, no change, or deterioration as per Section 8.4.3.4, ACQ-6 will also be summarized by treatment.

**Supportive outcome measure:** change from baseline to overall post-baseline mean of ACQ-6.

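### Rescue medication use and nights with awakening: the run-in diary baseline is not among the named covariates, which costs precision unless it is added

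*Protocol*

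**What the plan says.** For rescue use, section 8.5.7.8 states: "Total rescue medication use (average puffs/day) will be analyzed as the response variable by fitting a linear model to the data". It continues: "Treatment group will be fitted as the explanatory variable, and at least stratifying variables will be fitted as covariates". Results are to be given as least-squares means, their difference and a 95% confidence interval. Section 8.4.3.2 defines the quantity as a level: "Total rescue medication use, defined as the average number of inhalations (puffs) per day will be calculated as the outcome variable". It is not a change score.

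Nights with awakening are tied to this analysis: they "will be summarized and analyzed in the same way as rescue medication use".

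Both variables are recorded in the Asthma Daily Diary (section 5.2.2.1), and section 8.4.1.1 provides a baseline for such variables: "Baseline for Asthma Daily Diary variables will be the bi-weekly mean for data collected between study day -14 and -1". No analysis section uses that baseline for these two endpoints.

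Elsewhere the protocol does bring baseline in. Sections 8.5.7.2 to 8.5.7.4 add the baseline value to the change-from-baseline models for symptom score, AQLQ(S)+12 and ACQ-6. The ACQ-6 responder variable is analysed "using a logistic regression model with covariates of at least treatment, stratifying variables, and baseline value", and the AQLQ(S)+12 responder model has the same list. Home PEF, also in 8.5.7.8, is analysed as change from baseline.

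**The concern.** Among the modelled endpoints measured repeatedly on a continuous or count scale, rescue use and nights with awakening are the only two where baseline appears neither in the response nor among the named covariates. The symptom score comes from the same diary with the same baseline window, and its model includes the term.

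Randomization is stratified by periostin level, age group and region (section 3.5), so baseline rescue use and awakenings are not balanced by design. Inclusion criterion 14 is met by symptoms, or reliever use on more than 2 days, or a single awakening. Subjects can therefore enter with quite different levels on these two variables.

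At stake are the width of the confidence interval and the extent to which a chance difference at baseline shifts the observed treatment difference. This matters most in the biomarker positive population, the primary one, which section 8.2 puts at 20% to 35% of 770 subjects: 0.20 × 770 = 154 to 0.35 × 770 ≈ 270.

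**Working it through.** The protocol states no precision or power figure for these two endpoints, so there is none to reproduce.

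**Inputs.** 385 subjects per group and a biomarker positive share of 20% to 35% (section 8.2). The correlation ρ between the run-in mean and the on-treatment value, within strata, is not in the protocol; I assume 0.4 to 0.8.

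**Precision.** In a linear model, adding baseline multiplies the residual variance by 1 − ρ² and the confidence interval width by √(1 − ρ²). An analysis without it needs 1/(1 − ρ²) times as many subjects for the same precision.

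| ρ (assumed) | 1 − ρ² | CI width ratio | CI narrower by | 1/(1 − ρ²) |
|---|---|---|---|---|
| 0.4 | 0.84 | 0.92 | 8% | 1.19 |
| 0.5 | 0.75 | 0.87 | 13% | 1.33 |
| 0.6 | 0.64 | 0.80 | 20% | 1.56 |
| 0.7 | 0.51 | 0.71 | 29% | 1.96 |
| 0.8 | 0.36 | 0.60 | 40% | 2.78 |

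**Chance imbalance.** In SD units, the standard error of the baseline difference between arms is √(2/n), with n per arm. An unadjusted model passes an imbalance into the estimate at the regression slope of on-treatment on baseline. With equal SDs that slope is ρ.

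| Population | n per arm | One-SE imbalance (SD) | Shift at ρ = 0.4 | at 0.6 | at 0.8 |
|---|---|---|---|---|---|
| All subjects | 385 | 0.072 | 0.029 | 0.043 | 0.058 |
| 35% positive | 0.35 × 385 = 134.75 | 0.122 | 0.049 | 0.073 | 0.097 |
| 20% positive | 0.20 × 385 = 77 | 0.161 | 0.064 | 0.097 | 0.129 |

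**Level or change.** Let Y be the on-treatment value, B the baseline and T the treatment. The model Y − B = a + τT + γB rearranges to Y = a + τT + (γ + 1)B. The treatment difference τ and its interval are identical, so once baseline is a covariate the response need not be redefined. A change score without the covariate is a poorer remedy. With equal SDs its variance relative to the level is 2(1 − ρ): 1.20 at ρ = 0.4, 0.80 at 0.6 and 0.40 at 0.8, against 0.84, 0.64 and 0.36 with the covariate.

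**The case against.** The strongest objection is that the covariate list is open. The rescue-use model fits at least the stratifying variables, and the primary model in section 8.5.6 is worded the same way. The full covariate list of an other secondary endpoint is commonly settled in the SAP, which was not available for this review. A reader might infer that the protocol rules baseline out; it does not, and every loss shown above is conditional on nothing being added. Nor is a baseline covariate universal in this protocol: the written-out FEV1 model in 8.5.7.1, which home PEF follows, has none, although its response is a change.

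This objection limits the point but does not remove it. The AQLQ(S)+12 and ACQ-6 responder models use the same minimum-list wording and still name the baseline value. The minimum set for rescue use and awakenings is therefore thinner than for comparable endpoints, with no reason given.

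Three further inferences are tempting and not supported:

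- That the unadjusted comparison is biased. Randomization keeps it unbiased on average; only the realised estimate is affected.
- That imbalance passes through one-for-one. It passes at the regression slope, about 0.4 to 0.8 over the assumed range with equal SDs.
- That larger imbalance in the biomarker positive subset is itself a defect. Its expected size grows by 1/√0.35 = 1.7 to 1/√0.20 = 2.2, but so does the standard error, and the interval already reflects that.

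The protocol also gives no evidence on how strongly baseline predicts on-treatment rescue use or awakenings. It is also not true that the comparison carries all between-subject variation, since the stratifying variables are fitted.

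**Conclusion.** The point holds as an avoidable loss of efficiency. For two diary endpoints, section 8.5.7.8 does not commit to adjusting for a baseline that the trial already collects and defines, while the models for comparable endpoints use theirs. If the term is left out, the confidence interval is wider than it need be: adjustment would narrow it by 8% at a correlation of 0.4, 20% at 0.6 and 40% at 0.8. These figures rest on the assumed correlation and a linear model, and the pass-through figures also assume equal SDs at baseline and on treatment.

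The consequence is limited. Both are other secondary endpoints, neither appears in the nine-step testing hierarchy of section 8.5.1, and the results promised for rescue use are estimates with intervals, without a p-value. A reader might infer that a confirmatory claim is at risk; none is. This is a desirable improvement, not a necessary correction.

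**What to change.** In section 8.5.7.8, name the run-in mean (day -14 to -1, as defined in 8.4.1.1) of the same variable as a covariate, beside treatment and the stratifying variables, for rescue medication use and for nights with awakening. Leave both endpoint definitions as they are. If the SAP already includes the term, confirming that is enough.

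The cost is one clause. The data are already collected, and inclusion criterion 19 requires complete diary assessments on at least 10 of the 14 days before Visit 3, so the covariate should be available for nearly every randomized subject. The choice should be fixed before unblinding.
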